Innovation. The present study extends and compliments previous yoga research. Much of the current yoga literature is limited by small sample sizes and poor methodological rigor. In response to this need, the proposed study includes a randomized controlled design, with an active control condition that is matched for time/attention, social group interactions, attention, and expectancy. It features standardized and psychometrically sound assessment instruments, including blinded evaluation, and addresses the limited generalizability of previous samples by including both men and women with broad inclusion/exclusion criteria. Finally, it is set in a Veteran population, which is an understudied group in the published literature and may differ in important ways from non-military populations. Furthermore, the yoga intervention is a manualized Hatha yoga, which has been implemented in prior studies at this facility, and is reviewed for fidelity. Thus, the proposed project addresses an important need for high quality studies of yoga for PTSD. *The greatest innovation, however, lies in the evaluation and comparison of the Attention and Coping Models. Examination of these mechanisms will advance our understanding of the way in which a guided asana practice may impact PTSD, but will also inform yoga-based mental health treatment more broadly as these transdiagnostic processes are applicable to other mental health concerns.*

Research Design and Methods

The proposed study is a randomized controlled trial of Hatha yoga as compared to supportive physical activity in Veterans with PTSD. A sample of approximately 96 recruited (refer to Sample Size). Longitudinal outcome assessment will take place over approximately a 6 month period; refer to Table 1 for an overview of measures at each time point. A 3-month follow-up is planned because information about maintenance of change following the completion of a yoga intervention is important given the long-term follow-up data from the van der Kolk trial, which suggest that ongoing practice is critical continued clinical effects (Rhodes, Spinazzola, & van der Kolk, 2016).

Procedures

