Potential participants will be recruited from VA clinics (including primary care and mental health) and the community, following procedures that have been proven successful in our previous meditation and yoga trials. The initial contact for potential participants will be with a study recruiter/assessor, who will complete informed consent and conduct the evaluation for eligibility (see *Assessment*). After eligibility and consent are confirmed, the participant will complete the baseline assessment and then will have brief safety assessments every class; they will be asked to complete a total of 12 classes within 14 weeks. A follow-up will occur 12 weeks after the completion of the final class. No shows will receive a telephone follow-up. Participants will receive a payment for each assessment session (\$50 baseline part 1, \$50 baseline part 2, \$50 post-treatment part 1, \$50 post-treatment part 2, \$50 follow-up part 1, \$50 follow-up part 2 for a total of \$300; refer to Table 1).

Randomization will be done by the study statistician. In the initial phase of the trial, this was a 2:1 allocation to yoga and physical activity and took place at the individual level. Uneven allocation was planned to allow for sufficient power to accomplish the modeling proposed in Aim 2 (refer to *Sample Size*); given pandemic-related difficulties with accrual, however, the allocation will be reversed to 1:3 for the final months of the study to accomplish a minimum of 48/cell. The randomization table will be prepared prior to start of the study and revised for the new allocation strategy. Using an individual randomization strategy and continual group enrollment allows patients to begin treatment more quickly (i.e., as soon as the baseline evaluation is complete), which reduces attrition. This continual enrollment strategy is possible because the yoga and physical activity classes do not build from week to week; rather, every class provides multiple options for each pose/exercise to allow for individual differences, as is consistent with typical practice in the community. Further, sharing of personal information is minimized in this type of class, so newcomers are unlikely to cause discomfort among group members. Further, this strategy may support better retention. By allowing participants 14 weeks in which to complete 12 classes, participants will be able to make up missed classes to receive the full “dose.”

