Eligibility. The **Montreal Cognitive Assessment (MoCA)**; Nasreddine et al., 2005) is a brief (~10 minutes) clinician-administered cognitive screening test, which will be used to screen for cognitive impairment. If the score is < 22, which has been identified as an appropriate cutoff for psychiatric patients (Gierus et al., 2015), patients will be referred for additional evaluation and excluded, unless a qualified clinician provides clearance to participate. The **PTSD Checklist – 5 (PCL-5)**; Weathers, Litz, et al., 2013) will be used to quantify PTSD symptoms; individuals with a score of 33 or greater, the currently recommended cutoff for the instrument (National Center for PTSD, 2016), will be eligible for enrollment. Individuals with lower initial PCL-5 scores will be additionally evaluated using the CAPS if they carry a clinical diagnosis of PTSD. This self-report measure of PTSD is well-established for monitoring treatment-related change and has well-documented strong psychometric properties. The PCL-5 will be repeated at each assessment point for ongoing participant safety evaluation. Given that the TBN instructors will not be mental health professionals, [name], who is a privileged and licensed clinical psychologist with specialized training and 18 years of experience in treating Veterans with PTSD, will review these data (blinded to condition) on an ongoing basis to monitor adverse reactions. Absence of serious mental illness, untreated substance dependence, serious suicidality will be evaluated using the **Mini International Neuropsychiatric Interview (MINI 7.0)**; Sheehan et al 1998), which has been validated against the SCID and CIDI. The interview takes 15-30 minutes to complete and will be supplemented with questions to assess homicidality. Finally, the participant will be queried about use of mental health services, including pharmacotherapy, psychotherapy (type, modality, frequency and duration), complementary and alternative approaches and hospitalization using the **Emory Treatment Resistance Interview for PTSD (ETRIP)**; Dunlop, Kaye, Youngner, & Rothbaum, 2014). Psychotropic medication information will be collected and cross-checked against the electronic medical record. Mental health utilization will be used to characterize the sample and also to characterize behavioral changes associated with study participation at follow-up (e.g., continued yoga or exercise).

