Each outcome variable will be graphed versus time for each subject for all available time points (baseline, mid-treatment, post-treatment, follow-up) to evaluate what function of time best describes the data. Hypotheses 1a and 1b will be tested using the Mixed Effect Model (Hedeker, Gibbons, & Waternaux, 1999). This method is robust with respect to drop-out and missing data. These mixed models allow us to assess whether important estimates are dependent on missing data patterns, and provide overall estimates of effects by averaging over the various missing-data patterns (Hedeker et al., 1999). In addition, we will use the extension of the Pattern-Mixture Models (Guo, Ratcliffe and Ten Have, 2004), which allows subject-to-subject heterogeneity and assess if there is bias due to drop out or missing data. The Mixed Effect method has several advantages over more traditional analytic approaches such as a change score, end-point or repeated measures analysis of variance. It allows the inclusion of subjects with missing data or those who were terminated early in the study, without relying on data imputation procedures. This method provides an estimate of the individual variability around the population trend, the variability of the individual intercepts (baseline values) and slopes (changes across time), and the correlation between them. We will include a random intercept, a random effect for assessment time, and fixed effects for comparison groups and group-by-time interaction in the model. A fully saturated treatment by time model will be utilized for inference. Co-variance structure will be chosen based on Akaike's Information Criterion (AIC). Random group level treatment effects will also be evaluated for importance based on the model AIC. This allows for any group level effects to be incorporated into the model. Denominator degrees of freedom will be calculated using the Kenward-Roger small sample correction. Statistical significance will be determined by $p < .05$ for hypothesis 1a and $p < .01$ (.05/5 to correct for multiple comparisons) for hypothesis 1b.

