remove variables or create composites. Correlation coefficients among the outcomes for each mediator will be examined. Furthermore, the main effect of each outcome will be examined in the mixed effect model. Low correlated outcomes or outcomes that are highly (greater than .8) correlated with each other and/or low contribution in the model will be considered to be dropped from the model. The effect of mediators in the model can be calculated based on either the difference between two regression parameters ($\tau - \tau^2$) or the multiplication of two regression parameters ($\alpha\beta$) (MacKinnon, Warsi, & Dwyer, 1995). The variance estimates produced by the various methods are quite similar to each other and to the true value of the variance in situations involving continuous multivariate normal data and a continuous independent variable (MacKinnon et al., 1995). Although there is some evidence that the least model in the case-control study design setting this approach could provide biased estimations for the indirect effects (Wang et al., 2012), we believe the Sobel (1982) procedure to test for significant mediation is most appropriate approach for this study. Next we will use the formula provided by MacKinnon and Dwyer (1993) to determine the percentage of the intervention condition to primary outcome path that was accounted for by change in our mediator. We acknowledge that this method may not be supportable given the need to reduce sample size. If the study biostatistician determines that this is the case, she will utilize other strategies to analyze available data and generate testable hypotheses for future studies. The exploratory aim will be analyzed using similar approach. Data will be analyzed from all randomized subjects on whom we have a baseline assessment and at least one post-baseline evaluation. All statistical tests will be two-tailed. We will adjust p-values for multiple testing as appropriate.

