Sample size. We used the method provided by Hedeker, Gibbons, & Waternaux (1999) for the Random Regression Model and the RMASS program provided by Hedeker (2016) to estimate needed sample size for Aim 1. Medium effect size was selected based on finding from previous yoga trials (Wells et al., 2016) and was defined as a between-group difference increasing linearly from 0 at baseline to .5 SD units at the last time point. The minimum power estimation is based on sample size calculation for 10% and 20% attrition, correlations of 0.2, 0.5, and 0.8 between the repeated measures, and for medium and large effect sizes. We are confident that with the proposed total sample size of at least 48/arm would be sufficient to achieve a minimum 80% power for the primary aim.

Management

Management of this single-site study will be [name] responsibility. She has considerable experience in research management from small developmental grants (e.g., NCCIH R34) to a large multi-site consortium (INTRuST PTSD/TBI Clinical Consortium Deputy Director) and center of excellence (VASDHS CESAMH Associate Director). Administrative aspects of the project will be supported by [name], who has been [name] lead coordinator for more than a decade. [name] will coordinate scientific aspects of the project, holding regular meetings with the investigative team. [name], the study biostatistician, will work closely with [name] around data management and analysis. [name] will draw on his experience with yoga research to help with issues of recruitment, enrollment and retention. Drs. [name] (attention) and [name] (pain) will provide guidance in their relative areas of expertise. [name], who is a licensed clinical psychologist, also will be responsible for clinical oversight. The timeline of major study activities is presented in Table 2.

Table 2. Study Timeline

Year 1 (2018-2019)	Year 2 (2019-2020)	Year 3 (2020-2021)	Year 4 (2021-2022)	Year 5 (2022-2023)
Original Timeline				

Set-up	Recruitment (approx. 6/month x 30 mos)	Follow-up, data lock	Dissemination	Analyses	
Regulatory	Assessment				
Hiring	Intervention delivery, fidelity (12 groups)				
Training	Data management				
Recruitment	DSMB reporting				
Revised Timeline					

 ✓ Set-up ✓ Regulatory 	
 Recruitment (approx. 6/month x 30 mos) Assessment Intervention delivery, fidelity (12 groups) Data management DSMB reporting 	Follow-up, data lock	Dissemination	Analyses	

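### The sizing places the 0.5 SD difference at follow-up, 12 weeks after classes end, without justification, and the stated 80% minimum power does not hold for that effect at correlations of 0.2 or 0.5

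*Combined protocol and SAP*

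**What the plan says.** The Sample size paragraph of the Analytic Plan defines the medium effect as "a between-group difference increasing linearly from 0 at baseline to .5 SD units at the last time point". It considers attrition of 10% and 20%, correlations of 0.2, 0.5 and 0.8, and medium and large effects. It concludes that the trial "with the proposed total sample size of at least 48/arm" "would be sufficient to achieve a minimum 80% power for the primary aim".

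The visit is not named there, but other sections identify it. The Analytic Plan lists the time points in order, ending with follow-up. Table 1 schedules CAPS at baseline, post-treatment and follow-up, not mid-treatment. Procedures asks for 12 classes within 14 weeks and states: "A follow-up will occur 12 weeks after the completion of the final class".

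The opening of Research Design and Methods gives the reason for the follow-up: to learn whether change is maintained, because long-term data from one earlier yoga trial "suggest that ongoing practice is critical continued clinical effects". No classes are scheduled after the program. The treatment-use interview, described under Eligibility, is also to "characterize behavioral changes associated with study participation at follow-up (e.g., continued yoga or exercise").

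On testing, the Analytic Plan bases inference on a saturated treatment-by-time mixed model. "Statistical significance will be determined by $p < .05$ for hypothesis 1a", and "All statistical tests will be two-tailed". It does not say which contrast from that model decides 1a.

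**The concern.** A straight line to follow-up puts about half of the powered difference in a period when neither arm is being taught. A follow-up designed to study maintenance suggests a difference that is held or lost after classes, not one that doubles. The plan offers no argument for the growing shape.

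Two things are at stake. The first is whether 48 per arm supports the power claim for the effect that the paragraph defines. The second is which result will answer the primary aim. The only statement of where the effect is expected points to the last visit, while the model section leaves open whether the post-treatment difference, the follow-up difference or the joint interaction decides 1a. If these disagree, the choice could be made after the data are seen.

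**Working it through.** **Inputs from the plan.** n = 48 per arm; two-sided 0.05; difference 0 at baseline rising linearly to 0.5 SD; r = 0.2, 0.5, 0.8; attrition 10% and 20%; three CAPS visits.

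**Assumptions.** Compound symmetry, SD = 1 and known (normal approximation), visits at t = 0, 0.5, 1, monotone dropout spread evenly over the two later visits, no clustering by class.

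**Step 1: the difference at class end.** Classes end at week 12-14 and follow-up is at about week 24-26. The line gives 0.5 × 12/24 = 0.25 SD, or 0.5 × 14/26 = 0.27 SD.

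**Step 2: the plan's 80%.** For the group-by-linear-time slope without dropout, Var = (2/n)(1 − r)/Σ(t − t̄)². Here Σ(t − t̄)² = 0.5, so Var = 4(1 − r)/n, the same as for the baseline-to-follow-up change. Power = Φ(0.5/√Var − 1.96).

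- r = 0.2: Var = 3.2/48 = 0.0667, z = 1.936, power 49%.
- r = 0.5: Var = 2/48 = 0.0417, z = 2.449, power 69%.
- r = 0.8: Var = 0.8/48 = 0.0167, z = 3.873, power 97%.

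Generalised least squares with dropout gives 47/66/96% at 10% attrition and 44/62/94% at 20%. The 80% minimum is not reproduced at r = 0.2 or 0.5.

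The size needed for 80% without dropout is n = (1.96 + 0.842)² × 4(1 − r)/0.25 = 125.6(1 − r). That is 101 per arm at r = 0.2 and 63 at r = 0.5; with 20% attrition, 115 and 74.

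Variants do not rescue the claim:

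- Four equally spaced visits give 53/73/98% without dropout.
- A baseline-adjusted last-visit test at r = 0.5 reaches 81% without dropout and 72% with 20%. At r = 0.2 it gives 71% and 61%.

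The plan gives no number for a large effect. If it is taken as 0.8 SD, slope power is at least 83% over the whole grid.

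**Step 3: other shapes and contrasts.** Without dropout, the fitted slope over three equally spaced visits depends only on the difference at the end visits. For a joint 2-df interaction test, with a the difference at post-treatment and b at follow-up, the noncentrality is λ = n(a² − ab + b²)/(3(1 − r)). For (0.25, 0.5) and for (0.5, 0.25), λ = 48 × 0.1875/(3(1 − r)) = 3/(1 − r). For (0.5, 0.5), λ = 4/(1 − r).

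Power with 10-20% attrition:

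| Difference at baseline / post / follow-up | Test | r = 0.2 | r = 0.5 | r = 0.8 |
|---|---|---|---|---|
| 0 / 0.25 / 0.5 (as sized) | slope | 44-47% | 62-66% | 94-96% |
| | post-treatment change | 15-16% | 22% | 45-47% |
| | joint 2-df | 35-37% | 51-55% | 90-92% |
| 0 / 0.5 / 0.5 (maintained) | slope | 47-48% | 65-67% | about 96% |
| | post-treatment change | 47-48% | 65-67% | 96-97% |
| | joint 2-df | 47-49% | 67-70% | 97-98% |
| 0 / 0.5 / 0.25 (fading, assumed) | slope | 17% | 24% | 49% |
| | last-visit change | about 15% | 20-22% | 42-46% |
| | post-treatment change | 47-48% | 65-67% | 96-97% |
| | joint 2-df | 37-38% | 55-57% | 92-93% |

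**The case against.** The strongest reply is that the linear shape is a planning device for the random-regression sizing method, not a forecast for the weeks after classes, and that the planned saturated model imposes no trend. This largely stands. A reader might infer that a real end-of-treatment benefit would be reported as no efficacy. The documents do not support that: no slope or last-visit test is named for 1a, and a joint test in the saturated model has as much power under the fading shape as under the sizing shape.

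A reader might also infer that the sizing assumes a dose the trial does not give, or that the protocol itself predicts fading. Neither follows. The sizing assumes a trajectory of effect. Home practice is part of both programs, and participants may continue it. The remark about ongoing practice reports what data from one cited trial suggest, as a reason to measure maintenance. Nor is the linear shape optimistic in itself: 0.5 SD reached at class end and held gives the same slope power or slightly better.

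It can further be said that the last time point is not named and that the 80% may refer to the large effect. The first is true, but follow-up is the only reading that fits Table 1 and the listed time points. The second is possible, since the section on pilot effect sizes speaks of medium to large effects. But the paragraph defines only the medium effect numerically and states its minimum without restriction.

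**Conclusion.** The point holds as two linked faults. First, the assumed trajectory is unjustified and its visit unnamed; it implies about 0.25 SD at post-treatment. Second, the 80% minimum fails for the defined medium effect at two of the three planned correlations. The shortfall is large: more than 30 percentage points at r = 0.2 and roughly 15 to 18 at r = 0.5. Moving the 0.5 SD to post-treatment does not remove it.

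The unnamed contrast matters to the extent that the difference changes after classes. Under the assumed fading to 0.25 SD, power differs by a factor of about two to three between a slope or last-visit test and the post-treatment change. If the difference is maintained, the choice hardly matters. The documents do not settle which shape is right, so these figures are ranges and not a prediction. They rest on compound symmetry, evenly spread dropout, known variance and no clustering by class.

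**What to change.** In the Sample size paragraph:

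- Name the visit at which 0.5 SD is expected and give the reason for the trajectory between class end and follow-up.
- Replace the claim of at least 80% for a medium effect with power over the stated attrition and correlation grid. Compute it for the contrast that the saturated model will test, under a maintained and a fading shape.
- If the 80% is meant for a large effect, say so and give its size.

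In the Analytic Plan, name the contrast that decides 1a within the saturated model. The post-treatment CAPS difference is suggested, when the class program has just ended, with the follow-up difference reported as maintenance beside the record of continued yoga or exercise. Do not rest the conclusion on one linear slope across the taught and untaught periods.

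The cost is wording only, since the visits and the model are already planned. There are two downsides. The stated power becomes less favourable. And if the difference really did grow linearly to follow-up, a post-treatment contrast would have low power, as the second row of the table shows.

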attrition. It's generalizability to Veterans is also unknown. The other relatively large randomized evaluation of yoga included 64 women with chronic, treatment-resistant PTSD (van der Kolk et al., 2014). As compared to a health-education class, yoga was associated with greater change in PTSD symptoms (Cohen's $d = 1.07$). It is unknown, however, how these findings generalize to men. One uncontrolled trial involved Kripalu yoga, a form of hatha yoga, for active duty and Veteran participants. They observed large effect size pre-post change in symptoms (Cohen's $d = .77$), although this change was less than a benchmark that the authors calculated based on meta-analysis of published studies of active PTSD treatments (Johnston et al., 2015). In contrast, smaller studies have found no difference between yoga and a control condition (Mitchell et al., 2014; Thordardottir et al., 2014) or negligible effect on PTSD symptoms in Veterans ($n = 12$; Staples et al., 2013). Weighting the larger studies more heavily, we have powered the study to detect a medium to large effect size.

Ongoing Research

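### On the plan's own grid, 48 per arm gives about 44–47% (correlation 0.2) or 62–66% (correlation 0.5) power for the selected medium effect, not a minimum of 80%

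*Combined protocol and SAP*

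**What the plan says.** The Sample size paragraph at the end of the Analytic Plan uses a random regression model and the RMASS program for Aim 1. It states "Medium effect size was selected based on finding from previous yoga trials", and that this effect "was defined as a between-group difference increasing linearly from 0 at baseline to .5 SD units at the last time point". The calculation covers "10% and 20% attrition, correlations of 0.2, 0.5, and 0.8 between the repeated measures", for medium and large effects. The conclusion is that "at least 48/arm would be sufficient to achieve a minimum 80% power for the primary aim".

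The paragraph shows no power by scenario. It gives no SD value for a large effect, no number of visits, no test and no covariance structure. Pilot Effect Sizes puts the target more loosely: "we have powered the study to detect a medium to large effect size".

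The analysis model, described earlier in the Analytic Plan, has "fixed effects for comparison groups and group-by-time interaction in the model". It adds that "A fully saturated treatment by time model will be utilized for inference". "Co-variance structure will be chosen based on" AIC. The significance level is 0.05 for hypothesis 1a, and all tests are two-tailed. CAPS total is the primary outcome, and Table 1 schedules it at baseline, post-treatment and follow-up.

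**The concern.** A minimum over a grid cannot exceed the power in its weakest cell, and this grid includes the 0.5 SD effect at correlation 0.2. For a change from baseline, a low correlation between visits makes the comparison noisy, and 48 per arm looks too few for half an SD.

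This matters because the sentence is the only statistical support for the reduced sample. Feasibility cuts the target from 144 completers to about 96 enrolled because accrual was slow. The documents give no CAPS correlation, so a reader cannot tell which cell applies. If the 80% is taken at face value, a null result could be read as ruling out a medium effect that the trial had a substantial chance of missing.

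**Working it through.** **Inputs from the documents.** 48 per arm; difference 0, 0.25, 0.5 SD at the three CAPS visits; correlation r = 0.2, 0.5, 0.8; attrition 10% and 20%; two-sided 0.05.

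**Assumptions.** Equally spaced visits; SD 1 at each visit; compound symmetry as the base case; monotone dropout spread evenly over the post-baseline visits; normal approximation.

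**Hand check, no attrition.** Under compound symmetry the linear contrast over three visits equals last visit minus baseline:

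SE = √(2(1 − r)) × √(2/48), and power ≈ Φ(0.5/SE − 1.96)

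- r = 0.2: SE = 1.265 × 0.204 = 0.258; 0.5/0.258 = 1.94; power 49%
- r = 0.5: SE = 1.000 × 0.204 = 0.204; 0.5/0.204 = 2.45; power 69%
- r = 0.8: SE = 0.632 × 0.204 = 0.129; 0.5/0.129 = 3.87; power 97%

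So 80% is missed at r = 0.2 and 0.5 even with no dropout.

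**With attrition.** The SE of the slope difference comes from generalised least squares, with information summed over dropout patterns. As a bound, using completers only (43.2 or 38.4 per arm in the same formula) gives 45/64/96% and 41/59/93%. The full calculation must lie between these and the no-attrition values, and it does.

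Power at 0.5 SD for r = 0.2 / 0.5 / 0.8:

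| Reading | 10% attrition | 20% attrition |
|---|---|---|
| Compound symmetry, linear group-by-time | 47 / 66 / 96% | 44 / 62 / 94% |
| Compound symmetry, saturated model, last visit versus baseline | 47 / 66 / 96% | 44 / 62 / 94% |
| Compound symmetry, joint 2-df interaction | 37 / 55 / 92% | 35 / 51 / 90% |
| Compound symmetry, baseline difference fixed at zero | 71 / 78 / 97% | 67 / 74 / 96% |
| The same with four visits | 77 / 82 / 98% | 73 / 79 / 98% |
| AR(1), linear group-by-time | 41 / 49 / 80% | 39 / 47 / 77% |

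The AR(1) entry of 80% is 79.6% before rounding. Four visits without fixing the baseline difference gives 48–51% at r = 0.2 and 67–70% at r = 0.5. A t reference with 94 df lowers the first row by about a point or less.

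**Trying to reproduce the stated 80%.** It does not come out for 0.5 SD. If large means 0.8 SD (assumed), the linear test gives 83–100% under compound symmetry, with a minimum of 82.6% at r = 0.2 and 20% attrition. Under AR(1) it gives 76–99%.

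**What 80% would require (linear test, compound symmetry, 10% / 20% attrition).**

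- At 0.5 SD, per arm: 107 / 115 at r = 0.2; 68 / 74 at r = 0.5; 28 / 31 at r = 0.8.
- At 48 per arm and 0.5 SD: a correlation of about 0.65 / 0.68 (under AR(1), about 0.80 / 0.82).
- At 48 per arm, the detectable difference is (1.96 + 0.84) × SE. With no attrition at r = 0.2 this is 2.80 × 0.258 = 0.72 SD. With 10–20% attrition it is 0.75–0.77 SD at r = 0.2, 0.59–0.62 at r = 0.5 and 0.38–0.40 at r = 0.8.

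**The case against.** The strongest reply is that the 80% sentence names no effect size. Pilot Effect Sizes speaks of medium to large, the grid lists both, and the large-effect minimum of 82.6% fits the stated figure well. On that reading the sentence is badly labelled rather than miscalculated. That may be how the figure arose, but it does not rescue the text. The paragraph says medium was selected, defines only medium, and claims a minimum over a grid that contains it.

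A second reply is that the percentages depend on choices the plan does not state. This is true. At r = 0.2 and 0.5 SD, power under compound symmetry runs from about 44% to 77% across the linear and last-visit readings. The plan's random time effect is represented exactly by neither compound symmetry nor AR(1), so the decimals should not be pressed. AR(1) is also an added sensitivity case: one correlation between repeated measures most simply means a common one. The conclusion does not need AR(1), since every compound-symmetry reading leaves at least three of the six medium cells below 80%.

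Two further points stand. Power at r = 0.8 is adequate under compound symmetry (94–96%). And the sample was reduced because of accrual, with the power statement offered in support, so the size itself is not what is in dispute.

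**Conclusion.** The concern holds. For the effect the plan selects, the stated minimum of 80% fails in four of six cells under compound symmetry: 44–47% at correlation 0.2 and 62–66% at 0.5. A true 0.5 SD effect would be missed about 53–56% of the time at 0.2 and 34–38% at 0.5. The exact figures rest on three equally spaced CAPS visits, compound symmetry and a normal approximation. The finding that the minimum is below 80% does not depend on those choices among the readings tried, the best of which has a minimum of 73%. If a large effect was meant, the sentence is still wrong as written and must say so and give its value.

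**What to change.** Keep 48 per arm and remove the claim of a minimum 80% power for a medium effect. Replace it with power or the detectable difference by cell, naming the test, the visits and the covariance structure. For example:

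> With 48 per arm, three CAPS visits, 10–20% attrition and a two-sided 0.05 linear group-by-time test, 80% power corresponds to a last-visit difference of about 0.75–0.77 SD at correlation 0.2, 0.59–0.62 SD at 0.5 and 0.38–0.40 SD at 0.8 under compound symmetry, and 0.81–0.84, 0.72–0.75 and 0.50–0.52 SD under AR(1).

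State the SD value of the large effect, and make Pilot Effect Sizes and the Sample size paragraph agree on which effect the trial is powered for. If the joint 2-df interaction is the intended test, say so and give its lower power.

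Optionally, add 27% attrition as a sensitivity case (linear test, compound symmetry: 42/59/93% at 0.5 SD). The site's low-back-pain yoga trial, cited under Acceptability, retained 73% at 6 months.

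The change is to wording only, with no extra participants and no change to the analysis. The cost is a less favourable stated power.
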